#### **9.4. Randomization and Masking**

A stratified permuted-block randomization will be employed to randomize eligible subjects in a 1:1 ratio to either DE-117/Vehicle arm or Timolol Maleate arm. Two strata will be constructed based on age (adult:  $\geq$  18 years; pediatric:  $<$  18 years).

The randomization schedule will be generated and implemented using central randomization via Interactive Response Technology (Medidata BALANCE). Each randomized subject will receive numbered study medication kits as assigned by BALANCE.

This is a double-masked study. The subjects, Investigators, Examiners and Santen personnel involved in the conduct of the study will be masked to the study treatment. An authorized unmasked study staff member who is not the Investigator or Examiner at the investigative site will dispense and collect study medication(s) and will query about dosing compliance. Subjects will be instructed not to show the eye drop bottles or discuss the eye drop to either the Investigator or the Examiner or other study subjects. The active control treatment (Timolol Maleate) containers will be over-labeled and packaged in the same secondary package (e.g., cardboard carton) as the investigational treatment (DE-117). All subjects will receive a bottle labeled "morning" for the morning dose and a bottle labeled "evening" for the evening dose. However, the DE-117/Vehicle arm will receive the vehicle (i.e., "morning" bottle) at the morning dose, while the Timolol Maleate arm receives the active treatment (i.e., "morning" bottle) at the morning dose.

In case of a medical emergency, the Principal Investigator may reveal the treatment information by unmasking through Medidata BALANCE to know which treatment the subject has received.

The Principal Investigator (or his/her designee) should contact Santen, or Santen's designee, before taking this measure, if there is sufficient time. Santen, or Santen's designee, must be informed of all instances where the code is broken and of the reasons for such instances.

[figure not shown]
Additionally, the AE or SAE for which study treatment was unmasked should be reported to Santen Pharmacovigilance.

## 10. STUDY MEDICATION MATERIALS AND MANAGEMENT

### 10.1. Study Medication

[figure not shown]
#### 10.1.1. Investigational Product

DE-117 Ophthalmic Solution contains 0.002% or 0.02 mg/mL DE-117. Each 2.5 mL bottle of DE-117 Ophthalmic Solution 0.002% contains 50 µg of DE-117. In addition,

#### 10.1.2. Vehicle

The vehicle is identical to the investigational product but does not contain the active ingredient in DE-117.

#### 10.1.3. Active Control

The active control used in this clinical study, Timolol Maleate Ophthalmic Solution 0.5%, is supplied as a sterile, isotonic, buffered aqueous solution.

Timolol Maleate Ophthalmic Solution 0.5% contains the active ingredient, timolol 5 mg/mL and the preservative BAK 0.01%. Other ingredients include monobasic and dibasic sodium phosphate and purified water. The pH is adjusted to 6.5 to 7.5 with sodium hydroxide. See [Section 21.5](#).

### 10.2. Study Medication Packaging and Labeling

DE-117 Ophthalmic Solution 0.002% and DE-117 vehicle ophthalmic solution will be supplied as

Timolol Maleate Ophthalmic Solution 0.5% will be supplied as a 5 mL solution in a 5 mL white low density polyethylene bottle.

Each eye drop bottle will be placed in a unit carton. Four eye drop bottles/unit cartons of study medication will be placed in one kit. The eye drop bottles, unit cartons, and the kit will be labeled with the protocol number, kit number, storage conditions, and dosing instructions.

Kits dispensed at Visit 2 and Visit 4 (double-masked portion) will contain two (2) “morning” eye drop bottles and two (2) “evening” eye drop bottles of study medication.

An authorized unmasked study staff member, other than the Investigator or Examiner, will dispense and collect study medications. When collecting the study medications, the kit containing all the used and unused eye drop bottles will be sealed.

### **10.3. Study Medication Storage**

All study medication will be provided by Santen and will be stored in an appropriate secure area at the investigational site.

Study medications should be stored under refrigeration at 2° to 8°C (36° to 46°F), protected from light and stored upright. During the refrigeration storage, the Investigator (or his/her designee) will verify and record that the temperature was maintained at 2° to 8°C (36° to 46°F) using temperature recorder at least once every seven days at the investigational site, until the last subject has exited the study at the site. In the event of a temperature excursion or any study medications damaged during storage, the Investigator (or his/her designee) will notify Santen (or designee) and will not dispense the study medications until obtaining authorization from Santen (or designee).

Subjects will be reminded to store all dispensed eye drop bottles under refrigeration, protected from light and kept in unit cartons in an upright position. Study medications should not be frozen.

### **10.4. Study Medication Preparation**

The study medications will arrive at the site prepared for instillation.

### **10.5. Study Medication Administration**

During the Double-Masked Treatment Period subjects will instill one drop of study medication in each eye at approximately 20:00 (±60min) and 08:00 (±60min) daily for 3 months.

### **10.6. Study Medication Accountability**

The Principal Investigator is responsible for ensuring that an inventory is conducted upon receipt of the clinical supplies. The temperature chart recorder from the shipment will be deactivated, and the Investigator (or his/her designee) will verify that the temperature was maintained at 2° to 8°C (36° to 46°F) during transit. In the event of a temperature excursion or any study medications damaged during transit, the Investigator (or his/her designee) will notify Santen (or designee) and will not dispense the study medications until obtaining authorization from Santen (or designee). The receipt of clinical supplies form should be completed, signed, dated, and returned as directed. A copy must be maintained at the site for the Investigator's records.

The Investigator (or his/her designee) will keep a current record of the inventory, storage conditions and dispensing of all study medications. This record will be made available to Santen (or designee) for the purpose of accounting for all clinical supplies. Any significant discrepancy and/or deficiency must be recorded with an explanation.

All supplies sent to the investigational site must be accounted for and in no case will study medications be used in any unauthorized situation. It is the responsibility of the Investigator to

ensure that any used and unused supplies are available to Santen (or designee) for accountability purposes throughout the study.

### **10.7. Study Medication Handling and Disposal**

The used study medication kits will be stored at room temperature and the unused study medication kits will be refrigerated until final study medication accountability has been completed by Santen (or designee). Following final study medication accountability and reconciliation by Santen (or designee), all used and unused study medication will be returned to the assigned central drug depot.

### **10.8. Study Supplies**

Commercial urine pregnancy test kits and customized blood sample collection kits for the pharmacogenomics/genomics will be provided by Santen (or designee).

## **11. ASSESSMENT OF EFFICACY**

### **11.1. Efficacy Parameter**

The IOP (mmHg) measured in the study eye (identified at the baseline visit) is the efficacy measure for this study. The IOP at each scheduled time point (08:00, 10:00 and 16:00) will be evaluated at each post-baseline visit. Besides observed IOP measurements, change and percent change from baseline in IOP at each scheduled time point as well as the change and percent change from baseline in mean diurnal IOP will also be derived and evaluated.

## 12. ASSESSMENT OF SAFETY

### 12.1. Adverse Events and Serious Adverse Events

#### 12.1.1. Definition of Adverse Events

An adverse event (AE) is any untoward medical occurrence in a clinical trial subject. An AE does not necessarily have a causal relationship with the study medication. For this study, the investigational products are DE-117, DE-117 vehicle and Timolol. Regardless of relationship to the study medication, an AE can be a clinically relevant unintended sign (including an abnormal laboratory finding), symptom, or disease.

Any significant change in a subject's condition from the time that written informed consent is obtained, regardless of causality, is to be considered an AE. A clinically significant worsening in severity, intensity, or frequency of a pre-existing condition may indicate an AE.

An elective surgical procedure scheduled or planned prior to study entry that does not require an overnight hospitalization is not considered an AE, and the underlying diagnosis for the procedure should be captured in the medical history as a pre-existing condition. The surgical procedure should also include the term "elective" in all reports. An elective or planned hospitalization must be reported as an SAE.

The lack of efficacy of the study medication for the condition being investigated is not considered an AE unless a clinically significant change is assessed by the Investigator.

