#### 12.1.1.1. Assessment of Adverse Events

Investigators will seek information on AEs at each subject contact. Subjects should be asked using a general, non-direct question if there has been any change in their general health. Direct questioning and examination should then be performed as appropriate.

Severity of the AE should be assessed according to the following criteria:

**Mild:** No interference with the subject's daily activities; no medical intervention/therapy required.

**Moderate:** Possible interference with the subject's daily activities; no or minimal medical intervention/therapy required.

**Severe:** Considerable interference with the subject's daily activities; medical intervention/therapy required.

Regardless of severity, some events may also meet regulatory serious criteria. Refer to definitions and reporting of serious adverse events (SAEs) in [Section 12.1.2](#).

An Investigator who is medically qualified must make the determination of relationship (related or not related) to the investigational product for each AE or SAE. When determining relationship to study medication, the Investigator will consider any investigational products that a subject could be exposed to in this clinical trial. The Investigator should decide whether there is a reasonable possibility that the study medication caused the event, taking into account the following: a) evidence b) science-based rationale c) medical and clinical judgment d)

mechanisms of action e) biologic plausibility f) confounding risk factors (i.e., medical history, concomitant medications) g) temporal relationship h) dechallenge/rechallenge and i) lack of alternative explanation.

- The event may be recorded as **Related** to investigational product if:
  - There is a plausible temporal relationship between the onset of the AE and administration of the study medication
  - The AE abates or resolves upon discontinuation of the study medication or dose reduction and, if applicable, reappears upon rechallenge
  - The AE cannot be readily explained by the subject's clinical state, intercurrent illness, or concomitant therapies
  - The AE follows a known pattern of response to the investigational product
- Reporting the event as **Not Related** to study medication may be considered if:
  - There is good evidence that the AE has an etiology other than the investigational product (e.g., pre-existing medical condition, underlying disease, intercurrent illness, or concomitant medication)

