### **12.1.2. Serious Adverse Events**

#### **12.1.2.1. Assessment of Serious Adverse Events**

An AE is considered serious if it fulfills one or more of the following criteria:

- Death (i.e., the AE caused or led to death).
- It was life threatening (i.e., immediately life-threatening).
- It required or prolonged inpatient hospitalization.
- It resulted in a persistent or significant disability/incapacity (i.e., the AE resulted in a substantial disruption of the subject's ability to carry out normal life functions).

- It resulted in a congenital anomaly/birth defect in the offspring of a study subject who was exposed to study therapy prior to conception or during pregnancy.
- It is a medically significant event(s), which may include “sight-threatening events,” that may not meet any of the above serious criteria but may jeopardize the subject or require medical or surgical intervention to prevent one of the outcomes listed above.

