#### **12.1.2.2. Reporting Serious Adverse Events**

The SAE eCRF must be completed with as much information as is available within 24 hours of knowledge of the event.

To improve the quality and precision of acquired SAE data, Investigators should observe the following guidelines:

- Death: Death is an outcome of an event. The event that resulted in the death should be recorded and reported as the SAE.
- Hospitalizations for Surgical or Diagnostic Procedures: The illness leading to the surgical or diagnostic procedure should be recorded as the SAE, not the procedure itself. The procedure should be captured in the case narrative as part of the action taken in response to the illness.

Depending on the nature and seriousness of the AE, Santen may request additional documentation, for example, copies of the ophthalmic and medical records as well as results of laboratory tests. If the subject was hospitalized, a copy of the discharge summary may be requested.

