#### **14.8. Safety Analyses**

All safety outcome measures will be summarized descriptively for the Safety Population. The safety outcome measures include AEs, blood pressure and pulse rate, BCVA, slit-lamp biomicroscopy findings, ophthalmoscopy, iris color, eyelash, and eyelid.

AEs will be coded using the latest version of Medical Dictionary for Regulatory Activities (**MedDRA**). Subjects with any AEs will be tabulated by primary SOC and PT specified in the MedDRA. Similarly, subjects with any ocular and non-ocular AEs will be tabulated separately. AEs, ocular and non-ocular will also be summarized by relationship to treatment and maximum severity. In addition, SAEs and discontinuations due to AEs will be summarized.

Safety parameters listed in [Section 12.2.1](#) and [Section 12.2.2](#) will be summarized using descriptive statistics by actual treatment received. Changes from baseline in these safety parameters will also be summarized by treatment.

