4.4. Safety-Related Definitions

4.4.1. Adverse Event

Under Protocol 011710IN, an AE is defined as any untoward medical occurrence that occurs in a study subject, regardless of the causal relationship with the study treatment. An *on-study* AE can occur any time after the date of informed consent through the last study visit. An AE will be considered as *treatment-emergent* if the onset date of the AE occurred on or after the treatment start date till up to 2 days (twice the scheduled dosing interval) after treatment end date.

Treatment-emergent AEs (TEAEs) are a subset of on-study AEs. Both on-study and TEAEs will be collected, but only TEAEs will be tabulated.

The severity of each AE will be graded by the Clinical Investigator as Mild, Moderate, or Severe. AEs will also be rated by the Investigator as to their causality/relationship to the study drug.

Each AE will be classified into a system organ class (SOC) and coded to a preferred term (PT) using Medical Dictionary for Regulatory Activities (MedDRA), version 21.1 published in 2018.

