9.1.1. Ocular Inflammation

Subjects who developed AEs during the study with one of the following preferred terms will be included in the ocular inflammation summary:

- Anterior chamber cell
- Anterior chamber flare
- Eye inflammation
- Iridocyclitis
- Iritis
- Uveitis

Ocular inflammation leading to study drug discontinuation, requiring steroid treatment, or requiring NSAIDs treatment will be summarized at the subject level by frequency and percentage separately.

Ocular inflammation start time (in terms of study day) and duration of the AE will be summarized at the eye level using mean, standard deviation, median, minimum, and maximum by study eye and fellow eye separately. To allow for the computation of simple descriptive statistics, only subjects who develop ocular inflammation during the study will be used for the ocular inflammation start time summary, and only subjects who develop these AEs during the study and later resolved will be used in the duration of AE analysis.

All ocular inflammation AEs will be provided in a listing.

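### Protocol 12.1.1 makes every planned hospitalization an SAE, contrary to the protocol's own AE and SAE definitions

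*Protocol*

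**What the plan says.** Four places bear on the point.

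- **Protocol 12.1.1** opens with the definition: "An adverse event (AE) is any untoward medical occurrence in a clinical trial subject". It adds that a clinically significant worsening of an existing condition may indicate an AE. Elective surgery planned before study entry is exempt if it needs no overnight stay, and its diagnosis goes to medical history. The paragraph then ends: "An elective or planned hospitalization must be reported as an SAE".
- **Protocol 12.1.2.1** builds SAEs on AEs: "An AE is considered serious if it fulfills one or more of the following criteria". The hospital criterion is that the AE made an inpatient stay necessary or longer. SAP 4.4.1.1 repeats this, and counts an SAE whenever the investigator answers Yes to the seriousness question on the AE form.
- **Protocol 12.1.2.2**, on admissions for procedures, says: "The illness leading to the surgical or diagnostic procedure should be recorded as the SAE, not the procedure itself". The procedure itself goes into the narrative.
- **SAP 4.4.1** treats an AE as treatment-emergent "if the onset date of the AE occurred on or after the treatment start date" and no later than 2 days after treatment end. Only treatment-emergent AEs are tabulated. SAP 6.2.3 (Table 5) covers missing dates, and SAP 9.1 lists SAEs and non-treatment-emergent AEs.

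**The concern.** A hospital stay arranged before the subject joined, for a condition that has not changed, is not an untoward occurrence during the trial. Under the definitions it is not an AE, so it cannot be an SAE. Under the last sentence of that paragraph in 12.1.1 it must be one. A site cannot follow both.

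What is at stake is the meaning of the SAE count. SAP section 6 rules out statistical testing of safety measures, so the counts themselves are the safety evidence. In a 3-month eye-drop trial with about 200 subjects per arm they may well be small. A few entries that record scheduling rather than harm would then be visible in the tables, or would be absent from them, for reasons unrelated to either drug.

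**Working it through.** The protocol states no figure to reproduce. The check is a comparison of the rules, followed by one line of arithmetic.

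**Step 1: one operation, two settings.** Take an operation scheduled before consent for a stable condition.

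- As a day case, the 12.1.1 exemption applies: not an AE, and the diagnosis is medical history.
- With one overnight stay, the exemption no longer applies and the planned-hospitalization sentence makes it an SAE.

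The subject's condition is the same in both. Only the length of stay differs. Nothing has worsened, so the pre-existing-condition rule in 12.1.1 gives no ground for an AE. No AE caused or lengthened the stay, so the hospital criterion in 12.1.2.1 is not met either.

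**Step 2: what is recorded.** Under 12.1.2.2 the SAE term is the illness behind the procedure. Here that illness began before the trial. It is the same diagnosis that 12.1.1 sends to medical history for the day case.

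**Step 3: where the entry appears.** No section tells the site which onset date to use for such an entry. The SAP rules give:

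| Onset the site enters | Rule | Result |
|---|---|---|
| True onset of the illness, before treatment start | SAP 4.4.1 | Not treatment-emergent; listings only |
| Admission date, during treatment | SAP 4.4.1 | Treatment-emergent; in the SAE tables |
| Year only, an earlier year | SAP Table 5: set to the first day of that year | Not treatment-emergent; listings only |
| Left blank | SAP Table 5: taken as treatment-emergent | In the SAE tables |

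The same admission is tabulated under two of these entries and left out of the tables under the other two.

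**Step 4: size.** The planned arm size is 200 (Protocol 14.3.1). One subject with such an entry and no other SAE adds

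1 / 200 = 0.005 = 0.5 percentage points.

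The documents give no expected SAE rate. Assume 1% to 2%, that is 200 × 0.01 = 2 to 200 × 0.02 = 4 subjects per arm. The relative change in that arm's count is then:

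- one planned admission: 1/4 = 25% to 1/2 = 50%;
- two planned admissions: 2/4 = 50% to 2/2 = 100%.

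This range of 25% to 100% rests entirely on the assumed rate and the assumed number of admissions. The 0.5 points per subject does not.

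**The case against.** The strongest defence is that the sentence is deliberate over-reporting with labels. The sentence just before it asks for the term *elective* in all reports of the surgical procedure. The procedure is described in the narrative, SAEs are listed individually, and related events are tabulated separately as suspected adverse reactions. Adult exclusion criterion 9 bars ocular surgery during the study, so planned stays would mostly be non-ocular, and SAP 9.1 tabulates non-ocular events separately. Assignment is randomized and masked, so there is no reason to expect planned stays to favour one arm.

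Much of this stands, and it keeps the point small. It does not remove the conflict. The label attaches to the procedure, while 12.1.2.2 makes the illness the SAE term. SAP 4.4.1.1 counts the Yes answer and has no rule that separates planned stays. A reader of the listings could recognise these cases; the tables would not show them.

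Two stronger readings are tempting, and the documents do not support either.

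- *A reader might infer that the severity scale in Protocol 12.1.1.1 is equally defective, with no grade for treated events that do not considerably disturb daily life.* Moderate covers possible interference with "no or minimal medical intervention/therapy required", so such events can be graded. Some pairings have no literal match, such as considerable interference with no therapy. But the grades are paired descriptors for the investigator's judgement, and no text directs a wrong grade. Protocol 14.8 says AEs "will also be summarized by relationship to treatment and maximum severity", yet SAP 9.1 lists no severity tabulation. Ocular inflammation is reported by treatment need whatever its grade: cases "requiring steroid treatment, or requiring NSAIDs treatment will be summarized at the subject level".
- *A reader might infer that genuine SAEs are lost through onset dating.* They are not: SAP 9.1 lists SAEs and non-treatment-emergent AEs. Leaving a non-event out of the tables is the right result; the fault is that this depends on an unspecified date.

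**Conclusion.** The planned-hospitalization sentence in 12.1.1 contradicts the AE definition in the same section and the SAE definition in 12.1.2.1 and SAP 4.4.1.1. Followed as written, it puts non-events into the SAE data, and the onset date decides whether they are tabulated or only listed.

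The size is 0.5 percentage points per affected subject in a 200-subject arm. How many subjects would be affected cannot be told from the documents. The consequence is confined to descriptive safety counts: no test, no efficacy result and no stated figure changes, and nothing indicates a bias between arms. It is a low-impact error in a stated rule, worth correcting because the correction is short. The point does not extend to the severity scale.

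**What to change.** Reconcile Protocol 12.1.1, 12.1.2.1 and 12.1.2.2 by replacing the sentence in 12.1.1 with:

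> *A hospitalization planned before consent for a pre-existing condition that has not worsened since consent is not an AE or SAE and is recorded in medical history. If a worsening after consent required or prolonged the hospitalization, that worsening is the SAE, with its date as onset. Elective stays arranged after consent are assessed under 12.1.2.1.*

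The second sentence ties the SAE to a worsening that itself caused or lengthened the stay, so that a minor change before an already booked admission is not swept in. It also settles the onset date.

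SAP 3.1 says that enrollment had completed when the SAP was finalized, so an amendment may come too late. In that case, flag planned admissions before unmasking, using the narratives, the *elective* label and medical history, and report SAE counts with and without them.

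The cost is a short wording change with site guidance, or one flag and one extra set of SAE counts. No new assessments are needed, though a site query may be required where the date of planning is unclear. The downside is slightly less conservative SAE capture, because the site must judge whether the condition has worsened. Leave the severity grades as they are.
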